The Safety and Efficacy of the Transnasal Humidified Rapid-Insufflation Ventilatory Exchange (THRIVE) for Short Diagnostic Bronchoscopy Procedures

Study Protocol
NCT03086408

February 21, 2017

STUDY OBJECTIVES

1. DETERMINING THE SAFETY AND EFFICACY OF THRIVE FOR SHORT DIAGNOSTIC BRONCHOSCOPIC PROCEDURES.

THRIVE should improve glottic and tracheal exposure, operating conditions, decrease surgical time, and potentially lead to better patient outcomes. The safety of THRIVE for short diagnostic bronchoscopy has not been formally investigated, and will be explored in this study. With the patient anesthetized, apneic, and adequately oxygenated with THRIVE, the build-up of carbon dioxide in patient's blood (PaCO₂) and ensuing acute hypercapnic acidosis will be the main factors limiting the duration of THRIVE administration. At present, the rate of PaCO₂ rise with THRIVE has not been directly investigated, but is suggested to be 1.1 mm Hg per minute. It is expected that the short duration of diagnostic bronchoscopy procedures explored in this study will not lead to substantial rise of PaCO₂. The PaCO₂ rise to 70 mm Hg is considered a safe level for moderate hypercapnia in patients without significant comorbidities (see Exclusion Criteria).

2. DETERMINING POSSIBLE BENEFICIAL EFFECT OF THRIVE ON IMMEDIATE POSTOPERATIVE RECOVERY, OPIOD CONSUMPTION, AND FUNCTIONAL RECOVERY.

INCLUSION CRITERIA

Subjects presenting for short diagnostic bronchoscopy procedures under general anesthesia, including patients after bone marrow transplant (BMT).

EXCLUSION CRITERIA

1. Patients with significantly decreased myocardial function.
2. Patients with cardiac arrhythmias.
3. Patients with significant peripheral vascular disease.

STUDY PROTOCOL: THRIVE AND DIAGNOSTIC BRONCHOSCOPY

2

4. Patients with known significant cerebrovascular disease.
5. Patients with significant renal insufficiency.
6. Patients with electrolyte (K+, Ca++) abnormalities.
7. Patients with increased intracranial pressure or reduced intracranial compliance.
8. Patients with skull base defects.
9. Patients with pulmonary hypertension.
10. Immunocompromised patients.
11. Patients with significant chronic lung diseases.
12. Morbidly obese patients.
13. Patients with severe and poorly controlled gastsroesophageal reflux disease.
14. Patients with hiatal hernia and full stomach patients.
15. Patient's refusal to participate in the study.
16. Patients who do not understand English or mentally handicapped.

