17. Pregnant or breastfeeding patients.
18. "BMT patients with SpO2 < 90% on supplemental nasal oxygen up to 6 l/min, or those requiring non-rebreather mask to keep SpO2 > 90% will be excluded from the study."

PROTOCOL AT A GLANCE AND STUDY END-POINTS

1. Patients will be randomly assigned to either THRIVE or ETT/SGA (control group).
2. Anesthetic management is standardized for both groups.
3. Study end-points: per data collection sheet.

OPERATING ROOM PREPARATION

1. All drugs, airway supplies, eye tape, per routine.
2. 8.0 MLT ETT and SGA (i-Gel).
3. Precut large Tegaderm for securing ETT to the chin in left corner of mouth.
4. Four channel Alaris pump with:
 - a. NS carrier at 50 ml/hr
 - b. Propofol drip
 - c. Remifentanil drip
5. 20 ml NS syringe in line for chasing the induction and IVP drugs intraop. Please minimize IVF beyond 10 ml/kg total due to high incidence of urinary retention in male patients.
6. Working PNS with pads (make sure the battery is fresh).
7. Sedline or BIS.

STUDY PROTOCOL: THRIVE AND DIAGNOSTIC BRONCHOSCOPY

	THRIVE GROUP	CONTROL GROUP
PREOP and PREMEDICATION	
 • Obtain (check for) patient's consent. • Randomize the patient to either THRIVE or CONTROL group. • Obtain preop QoR15. • Peripheral IV, 20 g. • Midazolam 0.007 mg/kg incremental doses to achieve sufficient anxiolysis, not to exceed 0.025 mg/kg total dose. For elderly patients (70-80 y.o), limit total dose of Midazolam to 0.5 mg. 	
PRE-INDUCTION:	
Place standard ASA monitors, Sedline (BIS), and peripheral nerve stimulator (TOF ulnar nerve)
 
 • Apply THRIVE (FiO₂ 1.0) at 30 l/min. • Make sure the patient's head is elevated 30-40° (table in BACK UP position, not reverse Trendelenburg). 	
Preoxygenate.
 
 • IV fluid loading completed: 5 ml/kg. • IV Glycopyrrolate 0.2 mg if HR ≤ 50 bpm for elderly patients (70-80 y.o.). • Assure all bronchoscopy supplies are ready for immediate use in THRIVE group. • Both anesthesia and surgical time-outs completed.
INDUCTION	
 • IV Remifentanil 1 mcg/kg, Propofol 2mg/kg IV, Rocuronium 0. 6mg/kg IV. • Additional Remifentanil 0.5 mcg/kg and/or Propofol 0.5 mg/kg IV boluses, as required per hemodynamic responses and Sedline/BIS readings. 	

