MAINTENANCE (cont.)	
• Sedline/BIS-guided TIVA with Propofol/Remifentanil to maintain PSI 25-50 (BIS 40-60).• Maintain main IV at TKO. All IV bolus drugs are chased by 15 ml of NS using in-line 20 ml syringe.• TIVA dosing:
○ TIVA is carried in by Alaris NS carrier at 50 ml/hr.○ For normal weight patients, dose Prop/Remi infusions per total body weight.○ For obese patients ($\text{BMI} \geq 30$), dose Prop/Remi infusions per lean body weight (LBW). Simplified LBW formula: $\text{LBW} = \text{IBW} \times 1.2$; $\text{IBW} = 22 \times \text{Ht(m)}^2$.○ Propofol 80-150 mcg/kg/min, Remifentanil 0.05-0.3 mcg/kg/min. Optimize Remifentanil dose first.○ Rocuronium boluses 0.15 mg/kg, to maintain 0-1/4 TOF at ulnar nerve.• Treating hypertensive responses (MAP > 20 mmHg from baseline):
○ Remifentanil 0.5 mcg/kg and Propofol 0.5 mg/kg boluses q 2 min, as required per hemodynamic responses and Sedline/BIS readings○ Labetalol 0.07 mg/kg boluses q 10 min up to a total dose of 1 mg/kg, as required per hemodynamic responses and Sedline/BIS readings○ Fentanyl 0.5 mcg/kg IV bolus, total dose limit 1 mcg/kg, only if perceived need for additional analgesia after Remifentanil had been maxed out at 0.3 mcg/kg• Treating hypotensive responses (MAP < 20 mmHg from baseline):
○ Crystalloid loading 5 ml/kg x 1○ Ephedrine 5 mg IV if HR < 60 bpm, or Phenylephrine 100 mcg IV if HR > 60 bpm

STUDY PROTOCOL: THRIVE AND DIAGNOSTIC BRONCHOSCOPY

6

	
○ Vasopressin 1 unit IVP prn, as required○ Phenylephrine drip, as required, start at 0.3 mcg/kg/min, increase in 50% increments
EMERGENCE	
• Zofran 4 mg IV.• Reverse NMB with Sugammadex, as following: 2 mg/kg for TOF 1-2/4; 4 mg/kg for TOF 0/4, with posttetanic count of 1-2.• Discontinue TIVA and disconnect TIVA line upon completion of surgery.• Transport to PACU: FMO₂ at 6 l/min. 
• Maintain THRIVE at 70 l/min with jaw thrust ± oral airway as required, until return of spontaneous ventilation and consciousness.• Extubate per routine.

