STANDARDIZED POSTOP ORDERS	
• IV Fentanyl 25 mcg boluses q 5 min prn VAS ≥ 4, total dose 250 mcg.• PO Hydrocodone-acetaminophen (NORCO) 5-325 mg, 1 tab prn VAS ≥ 4, may repeat x 1.• If allergic to NORCO, Oxycodone-acetaminophen (PERCOCET) 5-325 mg, 1 tab prn VAS ≥ 4, may repeat x 1.• IV Demerol 10 mg for shivering only, may repeat x 1.• Treatment of PONV:
○ Zofran 8 mg IV x 1○ If no effect, and no contraindications, add IV Promethazine 12.5 mg x 1
PACU DATA COLLECTION	
• Obtain PACU data collection sheet and QoR15.
QUESTIONNAIRES and DIARIES	
• Pre- and post-procedural QoR15 questionnaires and post-procedural home diaries will be given to the patients. The BMT patients will receive QoR15 questionnaires, but will not keep the home diaries.

STUDY PROTOCOL: THRIVE AND DIAGNOSTIC BRONCHOSCOPY

7

THRIVE PROTOCOL	
PREOP	
• Randomize patient to THRIVE or ETT group.
PREINDUCTION	
• Start THRIVE @ 30 l/min immediately, before applying other OR monitors.• Maintain patient's head elevated 30-40°, with table in BACK UP, not reverse Trendelenburg position.
INDUCTION	
• THRIVE @ 70 l/min.• Place an oral intubating airway and maintain a jaw thrust for introduction of the fiberoptic scope by surgeon.
MAINTENANCE	
• Maintain THRIVE @ 70 l/min.• Maintain jaw thrust with the intubating oral airway in place for the duration of the procedure.• If surgery prolonged (over 30 min), consider converting to either SGA or ETT.
EMERGENCE	
• Maintain THRIVE at 70 l/min with jaw thrust ± oral airway as required, until return of spontaneous ventilation and consciousness.

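### Midazolam is titrated by judgement after randomisation, so premedication can differ by arm, in either direction, before either airway technique starts

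*Protocol*

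**What the plan says.** The PREOP and PREMEDICATION row of the protocol's two-arm table applies to both groups. After the consent check it reads "Randomize the patient to either THRIVE or CONTROL group". The preoperative QoR15 and the peripheral IV follow, and the last item is "Midazolam 0.007 mg/kg incremental doses to achieve sufficient anxiolysis, not to exceed 0.025 mg/kg total dose", with a further limit: "For elderly patients (70-80 y.o), limit total dose of Midazolam to 0.5 mg". The separate THRIVE PROTOCOL page also makes randomisation a PREOP step: "Randomize patient to THRIVE or ETT group".

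The airway techniques begin only in the next row, PRE-INDUCTION, with "Apply THRIVE (FiO₂ 1.0) at 30 l/min" in one arm and preoxygenation in the other.

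Under the protocol's at-a-glance heading stands "Anesthetic management is standardized for both groups". Objective 2 reads "DETERMINING POSSIBLE BENEFICIAL EFFECT OF THRIVE ON IMMEDIATE POSTOPERATIVE RECOVERY, OPIOD CONSUMPTION, AND FUNCTIONAL RECOVERY", and QoR15 and a data collection sheet are obtained in the PACU. The SAP describes unpaired t-tests and, for gender, a chi-square test. It mentions neither midazolam nor covariate adjustment. Neither document mentions blinding, concealment of the allocation, or who gives the premedication.

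**The concern.** Randomisation makes the groups comparable at the moment of assignment. Treatment given afterwards stays comparable only if it does not depend on the arm. Here a sedative is given after assignment, to an endpoint judged by the clinician, when the arm may already be known. If the doses differ by arm, a difference in early recovery would mix the effect of the airway technique with the effect of premedication. Because the dose follows allocation, adjusting for it in the analysis would not restore the randomised comparison.

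Unlike most discretion in an open-label anaesthetic trial, this part is avoidable. Premedication comes before anything that physically distinguishes the arms, so nothing in the midazolam rule requires the arm to be known when it is applied. Moving the QoR15 alone ahead of randomisation would protect the baseline score but would leave midazolam after allocation.

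**Working it through.** The plan states no figure on this point (no sample size, effect size, SD or allocation ratio), so there is nothing to reproduce. The check is the order of steps, the kind of target used, and the range that the rule allows.

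**Order of steps (two-arm table).** Consent check, randomisation, preoperative QoR15, IV, midazolam, then PRE-INDUCTION with THRIVE or preoxygenation. Consent at the head of the list and the IV ahead of the drug fit a reading in time order. The THRIVE PROTOCOL page agrees that randomisation is a PREOP step. Nothing in either document places it, or its disclosure, after premedication.

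**Kind of target.** In the MAINTENANCE rows, propofol and remifentanil are titrated to PSI 25-50 (BIS 40-60), and rocuronium to a train-of-four count. Midazolam has an increment and a cap, but no scale, fixed dose or fixed number of increments.

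**Range allowed by the rule.** Inputs from the protocol: increment 0.007 mg/kg, cap 0.025 mg/kg, and a 0.5 mg total at age 70-80. Body weight is not given. I assume 70 kg and show 50-100 kg.

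- Increments under the cap: 0.025 / 0.007 = 3.57, so 0 to 3 full increments. Three come to 3 × 0.007 = 0.021 mg/kg; a fourth would reach 0.028 mg/kg, above the cap.
- At 70 kg: one increment is 0.007 × 70 = 0.49 mg, three are 1.47 mg, and the cap is 0.025 × 70 = 1.75 mg.
- Over 50-100 kg: one increment runs from 0.35 to 0.70 mg, and the cap from 1.25 to 2.5 mg.
- At age 70-80: 0 to 0.5 mg, about one increment at 70 kg. Above 0.5 / 0.007 = 71.4 kg, one full increment would exceed this limit, so the sponsor should reconcile the two statements.

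**Difference in arm means.** For patients of 70 kg outside the elderly limit, a mean difference of 0.49 mg arises if every patient in one arm receives one increment fewer than a counterpart in the other. The maximum of 1.75 mg would need one arm at the cap throughout and the other given none, which is a bound and not an expectation.

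**From dose to outcome.** The documents give no relation between midazolam dose and emergence time, PACU measures or QoR15. That midazolam can affect early recovery at all is general pharmacology. The calculation therefore stops at milligrams.

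**The case against.** The strongest case on the other side has five parts.

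1. **Knowledge of the arm is inferred.** The protocol does not say who gives midazolam or when the allocation is disclosed. This stands: the inference rests on step order and on the absence of any blinding text. It supports saying that the dose can depend on the arm, not that it does.

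2. **The direction is unknown.** A reader might infer that THRIVE patients would receive less, because they have no airway device and are kept on THRIVE "until return of spontaneous ventilation and consciousness", and that the bias would favour THRIVE. The documents do not support that. Control patients must also recover before extubation, both arms receive the same neuromuscular blockade and intravenous anaesthesia, and reversal is listed without naming an arm. High nasal flow is also applied to awake patients in the THRIVE arm, which could prompt more anxiolysis. Either direction is possible.

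3. **Management is declared standardised.** For midazolam this amounts to a common increment and cap, not a common dose. The common depth target in maintenance may offset some of a premedication difference, but the documents do not show how much.

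4. **Wider discretion remains later.** Propofol may run at 80-150 mcg/kg/min and remifentanil at 0.05-0.3 mcg/kg/min (six-fold), with boluses as needed, once the airway technique is visible. This stands as a limit on what the fix achieves. It is no reason to keep a source of bias that a change of step order can remove.

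5. **Co-medication may belong to the strategy.** If the question were THRIVE as a whole anaesthetic strategy, dosing driven by allocation could count as part of it. The documents define no estimand that says so or excludes it. The statement that anaesthetic management is standardised points more towards a comparison of airway techniques.

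**Conclusion.** The point holds as a bounded, avoidable opening for co-intervention bias. Midazolam is listed after randomisation, is titrated to an unmeasured endpoint, and is given with no blinding described, before either airway technique starts. At an assumed 70 kg the discretion spans 0 to 1.75 mg (0.49 mg per increment, 1.47 mg for three), and 0 to 0.5 mg at age 70-80. The conclusion assumes that the bullets run in time order and that the premedicating clinician can know the arm.

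A reader might infer more from this than the documents support. They do not show that doses differed by arm, that recovery results are biased in favour of THRIVE, or by how much. Objective 2 sets out to determine a possible benefit and does not claim one. The study end-points are deferred to a data collection sheet that is not among the documents, so midazolam dose may already be recorded. The change is worth making because it is cheap and alters no dose, not because a large bias has been demonstrated.

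**What to change.** In both the PREOP and PREMEDICATION row and the PREOP row of the THRIVE PROTOCOL page, state that the allocation is opened only after the preoperative QoR15 and premedication are complete, on entry to the operating room and before THRIVE or preoxygenation is applied. Leave the midazolam rule as it is. Add to the SAP a descriptive table of midazolam dose by arm, wherever the dose was recorded.

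The cost is practical. THRIVE equipment must be ready for every case; the tube and supraglottic airway are already on the operating room preparation list. The THRIVE PROTOCOL page starts THRIVE before the other monitors are applied, so the interval for opening the allocation is short and should be written into the sequence.

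The SAP is dated June 2020 and written in the past tense. If enrolment is complete, the step order can no longer be changed. What remains is the table by arm and a sentence in the report saying that premedication followed randomisation without described blinding. Similar doses in the two arms would be reassuring on this point; an imbalance should be reported as a limitation on the recovery comparison, not adjusted away. In either case the open-label dosing of propofol and remifentanil is left as it is.

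### The 0.5 mg midazolam limit covers ages 70-80 only, but no upper age for eligibility is stated, so read literally it does not cover an eligible patient over 80

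*Protocol*

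**What the plan says.** The premedication row of the protocol's main table has three parts on midazolam. Dosing is titrated: "Midazolam 0.007 mg/kg incremental doses to achieve sufficient anxiolysis". There is a general ceiling: "not to exceed 0.025 mg/kg total dose". There is a lower limit for older patients: "For elderly patients (70-80 y.o), limit total dose of Midazolam to 0.5 mg".

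The same age band appears once more, in the glycopyrrolate instruction of the pre-induction row, whose condition reads "50 bpm for elderly patients (70-80 y.o".

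Eligibility is open as to age. The inclusion criterion takes "Subjects presenting for short diagnostic bronchoscopy procedures under general anesthesia", with bone marrow transplant patients included, and none of the 18 numbered exclusions concerns age. The SAP says nothing about age limits or dosing. The protocol's overview section says that "Anesthetic management is standardized for both groups", and the midazolam rule stands in the row shared by both arms.

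**The concern.** A reduced sedative limit for the elderly would be expected to apply from some age upwards. This one has a closed upper end at 80, and eligibility has none. Followed to the letter, the permitted maximum falls at 70 and rises again after 80, so the oldest eligible patients have a higher ceiling than those aged 70-80.

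What is at stake is patient safety, in a small way. It is the only drug dose limit in the protocol that depends on age, and the first study objective includes safety. Because management is meant to be standardized, the written rule is what staff are asked to follow.

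**Working it through.** **Inputs.** From the premedication row: limit of 0.5 mg at ages 70-80, general ceiling of 0.025 mg/kg, step of 0.007 mg/kg. Body weight is not in the documents; I assume 70 kg, with a range of 50-100 kg.

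**Which rule applies over 80.** The inclusion criterion has no age bound and the exclusions have no age item, so a patient of 81 is eligible as written. The 0.5 mg limit names ages 70-80. Read literally, only the general ceiling is left.

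**Permitted maximum.** Ceiling = 0.025 mg/kg × weight; difference = ceiling − 0.5 mg.

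| Weight | Ceiling | Difference from 0.5 mg | Ratio to 0.5 mg |
|---|---|---|---|
| 50 kg | 0.025 × 50 = 1.25 mg | 0.75 mg | 2.5 |
| 70 kg | 0.025 × 70 = 1.75 mg | 1.25 mg | 3.5 |
| 100 kg | 0.025 × 100 = 2.50 mg | 2.00 mg | 5.0 |

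The two limits are equal at 0.5 / 0.025 = 20 kg, so they differ at all the weights considered here.

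**Full titration steps.** The ceiling holds 0.025 / 0.007 = 3.57 steps, so at most three full ones. Dose = steps × 0.007 mg/kg × weight; the excess over 0.5 mg is in brackets.

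| Full steps | 50 kg | 70 kg | 100 kg |
|---|---|---|---|
| One | 0.35 mg (none) | 0.49 mg (none) | 0.70 mg (0.20) |
| Two | 0.70 mg (0.20) | 0.98 mg (0.48) | 1.40 mg (0.90) |
| Three | 1.05 mg (0.55) | 1.47 mg (0.97) | 2.10 mg (1.60) |

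One step equals 0.5 mg at 0.5 / 0.007 = 71.4 kg. At 70 kg the gap therefore matters only if a second step is given; above 71.4 kg one full step already exceeds 0.5 mg.

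**The case against.** The strongest reply is that the gap needs an unnatural reading. The sentence is about elderly patients, and an anesthesiologist would probably treat an 85-year-old as elderly whatever the bracket says. Titration to effect limits the dose further: at 70 kg one step stays under 0.5 mg, and three full steps reach 1.47 mg, short of the 1.75 mg ceiling. This stands, and it is why the severity is low. It does not remove the point: if everyone would read the rule as 70 and over, the protocol should say that.

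A second reply is that enrolment was meant to stop at 80. The repeated 70-80 band in the glycopyrrolate line is consistent with this, and the dosing rule would then be complete. But no such limit is written, and the documents do not settle which was meant. On that reading the omission is in the eligibility criteria, and one line still has to change.

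A third reply is that there may be little left to correct. The SAP, dated June 2020, is in the past tense, so dosing may be finished. That is fair; the correction would then mainly serve further use of the protocol.

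A reader might infer from the ratio of 3.5 that patients over 80 were given, or would be given, 3.5 times the dose. The documents do not support this: the ratio compares two ceilings, dosing is titrated, and no doses given are reported.

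**Conclusion.** The point holds as a gap in a stated dosing rule. Read literally, an eligible patient over 80 has a permitted maximum of 1.75 mg at an assumed 70 kg (1.25-2.50 mg at 50-100 kg) against 0.5 mg at ages 70-80, contrary to what the rule is evidently for. That purpose is inferred from the rule's content; neither document states it.

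The severity is low. The number of patients over 80 is not stated and may be zero. A reader might also infer that the general ceiling is unsafe over 80, or that the gap distorts the trial's results. Neither follows: the documents say nothing on the safety of 0.025 mg/kg at that age, and the rule applies equally to both arms, so endpoints and the between-arm comparison are untouched.

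**What to change.** In the midazolam sentence, replace the age group with *patients aged 70 years and over* and keep the 0.5 mg limit as it is. Use the same age wording in the glycopyrrolate instruction. That instruction is not a dose cap and no dosing error is claimed in it, but if it kept the 70-80 band, two definitions of elderly would stand in adjacent rows, and a patient over 80 with a low heart rate would still fall outside it. The cost is one phrase in each of two lines, with no effect on endpoints or analysis.

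If enrolment was meant to stop at 80, leave both lines alone and add that age limit to the exclusion criteria. This costs one line but could narrow the population as now written; the documents state no sample size, so the effect on recruitment cannot be checked.

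### As printed, the remifentanil threshold for intraoperative fentanyl is a dose (0.3 mcg/kg), while the only matching limit is an infusion rate (0.3 mcg/kg/min)

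*Protocol*

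**What the plan says.** All the relevant text is in the protocol; the SAP does not touch the point.

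- **Fentanyl condition** (MAINTENANCE (cont.), treating hypertensive responses): the step is "Fentanyl 0.5 mcg/kg IV bolus, total dose limit 1 mcg/kg", to be used "only if perceived need for additional analgesia after Remifentanil had been maxed out at 0.3 mcg/kg".
- **Infusion range** (same row, TIVA dosing): "Propofol 80-150 mcg/kg/min, Remifentanil 0.05-0.3 mcg/kg/min. Optimize Remifentanil dose first".
- **Rescue boluses** (same row, first step for hypertensive responses): "Remifentanil 0.5 mcg/kg and Propofol 0.5 mg/kg boluses q 2 min", as required.
- **Induction** (INDUCTION row, common to both groups): "IV Remifentanil 1 mcg/kg, Propofol 2mg/kg IV", with "Additional Remifentanil 0.5 mcg/kg and/or Propofol 0.5 mg/kg IV boluses" as required.
- **Standardization** (PROTOCOL AT A GLANCE AND STUDY END-POINTS): "Anesthetic management is standardized for both groups".

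No section defines 0.3 mcg/kg as a single-dose or cumulative limit for remifentanil.

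**The concern.** The fentanyl line is an operative decision rule: it tells the anesthesia provider when a second opioid may be added. Its threshold carries the same number as the top of the infusion range but a different unit. The printed unit is not meaningless, because mcg/kg without a time term is how the protocol writes its remifentanil boluses, at induction and in the hypertension list itself. A provider who takes the line at face value would find the remifentanil condition already met once anesthesia has been induced. A provider who assumes a rate would wait until the infusion is at the top of its range.

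Two readings of one rule sit badly with the statement that anesthetic management is standardized. Opioid consumption is also named in objective 2, so a rule about giving an opioid before the PACU should be unambiguous.

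**Working it through.** The check is a comparison of units and simple ratios. No sample size, power or error rate is involved, and there is no computed figure in the plan to reproduce.

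**Inputs, all from the protocol**
- Printed threshold: 0.3 mcg/kg (fentanyl line)
- Infusion range: 0.05 to 0.3 mcg/kg/min (TIVA dosing)
- Induction dose: 1 mcg/kg, both groups (INDUCTION)
- Single bolus: 0.5 mcg/kg (INDUCTION and hypertensive responses)

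**Step 1: threshold read as printed (a dose)**
- Induction dose / threshold = 1 / 0.3 = 3.3
- One bolus / threshold = 0.5 / 0.3 = 1.7
- Time for the infusion alone to deliver 0.3 mcg/kg: 0.3 / 0.05 = 6 min at the bottom of the range; 0.3 / 0.3 = 1 min at the top

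Whether 0.3 mcg/kg is taken as a single dose or a running total, it is passed at induction. If the induction dose is left out of the count, one rescue bolus or 1 to 6 minutes of infusion passes it.

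**Step 2: could the weight basis rescue the printed figure?** The protocol gives a dosing weight for infusions but none for boluses. The least favourable combination puts the induction dose on ideal body weight (22 × height², the protocol's own formula) and the threshold on total body weight (BMI × height²). Height cancels:

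ratio = (1 × 22) / (0.3 × BMI)

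- BMI 30: 22 / 9 = 2.4
- BMI 40: 22 / 12 = 1.8
- Ratio falls to 1 at BMI = 22 / 0.3 = 73

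Morbidly obese patients are excluded, so the weight basis does not change the result.

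**Step 3: threshold read as a rate (0.3 mcg/kg/min)**
The induction dose no longer meets it. The condition is met only when the infusion has been raised to the top of its stated range, so it does restrict. This shows what the other reading gives; it does not say which figure is right.

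**The case against.** The strongest reply is that nobody would read the line literally. Describing a drug as maxed out points naturally to the top of a range; the number matches the range in the same table row; that range comes with an instruction to optimize remifentanil first; and the literal reading makes the clause pointless. This stands as an account of the likely intent. It does not remove the inconsistency, because the line is an operative threshold and its printed unit is in live use for boluses nearby.

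Three stronger readings are tempting, and the documents support none of them.

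- **That fentanyl is unrestricted.** Only the remifentanil part of the condition falls away. The step still applies only to a hypertensive response (mean arterial pressure more than 20 mmHg from baseline), still requires a perceived need for more analgesia, and is still capped at 1 mcg/kg in total.
- **That even a rate would not be a real ceiling, because of the boluses.** Boluses of 0.5 mcg/kg every 2 minutes add 0.5 / 2 = 0.25 mcg/kg/min, so an uninterrupted series on top of the maximum infusion would give 0.30 + 0.25 = 0.55 mcg/kg/min. But the boluses are given as required, and the protocol nowhere says that 0.3 mcg/kg/min caps total remifentanil. A maximum infusion rate and as-required boluses can coexist; this is not a contradiction.
- **That the slip biases the comparison in objective 2.** Judgement of need by a provider who knows the arm is present under either unit. Any difference between arms in hypertensive responses would be an assumption, and its direction is unclear: controls have an SGA or ETT placed, while THRIVE patients have sustained jaw thrust and an oral airway. The documents also do not say whether opioid consumption includes intraoperative doses.

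**Conclusion.** The unit inconsistency is certain. As printed, the remifentanil threshold is exceeded 3.3 times by the induction dose in every patient dosed per protocol, and 1.7 times by one bolus on the same weight basis, so it does no work. That consequence rests on the literal text alone; a dropped per-minute term is the more likely explanation, and with it the condition would bind.

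The severity is minor. What can be said is that one clause of a standardized regimen can be read in two ways. The documents contain no information on how providers read it, how often fentanyl was given, or whether its use differed by arm.

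**What to change.** The investigators should reconcile the unit of the fentanyl condition with the TIVA infusion range and the bolus doses, so that the same rule applies to all patients under the stated standardized management. Which limit is correct is for them to decide. The cost is a one-line correction.

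The SAP is dated June 2020 and written in the past tense, so the correction may come too late to affect conduct. In that case, a sentence in the trial report saying how the condition was applied would serve.

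Optionally, intraoperative fentanyl could be reported by arm beside PACU opioid use, to help interpret objective 2. This depends on the doses having been recorded. The end-points are deferred to a data collection sheet that is not among the documents, so neither availability nor cost can be confirmed.
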